10.5.1 Patient Reported Outcomes

The PRO instruments to be measured in this study are described below. These measures will be administered in this study at 3 timepoints: Screening or Baseline Visit, 6-month visit, and Completion/Termination Visit, whereas the EQ-5D, Patient Activity Level, and Health Resource Use will be measured at each study visit before study specific procedures are started. Note that due to the unavailability of linguistically validated translations of certain PRO measures in certain countries, some of these questionnaires may not be administered in all countries participating in this study. In addition, subjects who are younger than the minimal age limit required for these assessments will not be required to complete the assessment.

1. **Haemo-SYM Questionnaire** – This is a self-administered, validated questionnaire designed to assess symptom severity in subjects with hemophilia. This measure contains 17 items and includes 2 domains: Bleeds and Pain. Scores for each of these 2 domains can be calculated, with higher scores indicating more severe symptoms. This questionnaire will be administered only to subjects \geq 18 years of age.
2. **Short Form-36 (SF-36)** – The SF-36 is a self-administered, validated questionnaire designed to measure generic HRQoL. This 36-item questionnaire measures 8 domains, including: Physical functioning, Role-physical, Bodily pain, General health, Vitality, Social functioning, Role emotional, and Mental health.

Two summary scores can be calculated, the Physical Component Score, and the Mental Component Score. Additionally, scores can be calculated for each of the 8 domains. Higher scores indicate better health status. This questionnaire will be administered only to subjects ≥ 14 years of age.

3. **EQ-5D Questionnaire** – The EQ-5D is a self-administered, standardized measure of health status that provides a generic measure of health for clinical and economic appraisal consisting of the following 5 dimensions: mobility, self-care, usual activities, pain/discomfort, and anxiety/depression each with 3 levels. There is an additional EQ visual analog scale to record how good or bad their health state is.
4. **Patient Activity Level**
Subjects will also be asked to estimate their activity levels. This will consist of a few questions asking subjects to rate their current level of activity. These data will be collected for all age groups.

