Purpose for Change: 1) To also handle the case that the trough levels used for dose adjustment were due to different doses. The former formula would only handle the case of the same dose being used for all infusions as required per protocol. 2) To ensure that the dose is continuously aligned with the subject's weight changes, if applicable.

11. **Section 8.7.7, Treatment of Bleeding Episodes**
Description of Change: The anticipated recovery to be used in the absence of an individual recovery has been revised.
Purpose for Change: To be consistent with already approved prescribing information.

12. **Section 10.5.1, Patient Reported Outcomes**
Description of Change: Description of EQ-5D questionnaire amended to reflect 3 levels for each of the 5 measured dimensions.
Purpose for Change: Correction of error in original text.

13. Section 11.1.3, Hemophilia Joint Health Score (HJHS);

Section 11.1.4 X-ray of Impaired Joints;

Section 21.2, Detailed Flow Diagram of Study Procedures, Visits at Study Site;

Section 21.3, Schedule of Study Procedures and Assessments;

Section 23.3, Radiologic Classification of Changes

Description of Change: 1) The X-ray of an impaired joint was removed from Section 11.1.3 HJHS and a new Section regarding the conductance of an X-ray was added. 2) Definition for impaired joint requiring conductance of an X-ray was provided based on the HJHS scoring system. 3) Already existing X-rays of impaired joints not older than 12 months can be used. The repeat X-ray of the impaired joint after 12 months was removed. 4) The Pettersson Score was added to describe the radiologic findings.

Purpose for Change: 1) To account for the fact that X-ray is not part of the HJHS. 2) To provide a definition for a clinically impaired joint. 3) No radiologic changes are expected after 12 months of prophylactic treatment. 4) To have a consistent description of radiologic findings of the impaired joint.

14. Section 13.1, Immunogenicity;

Section 13.2.1.1, Serious Adverse Event

Description of Change: 1) In order to meet the definition of an SAE, the FVIII inhibitor has to be confirmed at the central laboratory. 2) Details were provided when to evaluate FVIII IgG subclass 1-4 and IgA, and IgE antibodies to FVIII and PEG-FVIII.

Purpose for Change: 1) To account for different threshold levels at the various local laboratories. 2) To provide instructions when to assess FVIII IgG subclass 1-4 and IgA as well as IgE antibodies.

15. Section 13.9.1.1, Blood Type

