7.2.4 Euro Quality of Life-5 Dimension (EQ-5D) Questionnaire

The EQ-5D questionnaire is a self-administered, standardized instrument for the measurement of health status regards quality of life.

The EQ-5D comprises 5 dimensions of health (mobility, self-care, usual activities, pain/discomfort, and anxiety/depression). For each dimension, respondents select which statement best describes their health on that day from a possible 5 options of increasing levels of severity with a score from 1 to 5 (no problems, slight problems, moderate problems, severe problems, and extreme problems). The severity score on each individual dimension is combined to form a unique EQ-5D health state as a 5-digit code allowing for a total of 3125 health states.

For example, state 11111 indicates no problems on any of the 5 dimensions. These data will be converted into a weighted health state index by applying scores from EQ-5D value sets elicited from general population samples (the base case will be the United Kingdom valuation set, with other country value sets applied as available).

In addition to the descriptive system, subjects also assess their health on the day of assessment on a visual analogue scale (VAS), ranging from 0 (worst imaginable health) to 100 (best imaginable health). This score is reported separately.

Information on the EQ-5D is obtained from electronic subject diaries as supplied by the third party vendor eRT.

The following derivations will be made based of the subject diary reported results:

- The unique 5-digit health code per subject per assessment which is obtained by concatenating the individual scores of the five domains in their order as presented on the questionnaire itself.
- The utility total score should only be derived and calculated as follows if none of the 5 component scores are missing (depending on the country/region applicable) using both “VAS” value sets and the TTO value sets:
 - For all countries excluding Germany, the utility total score using “VAS” value sets can be derived as:

Utility Total Score

$$\begin{aligned}
 &= W_{FH} + W_{N2} \times N2 + W_{N3} \times N3 + W_{MO2} \times MO2 \\
 &+ W_{MO3} \times MO3 + W_{SC2} \times SC2 + W_{SC3} \times SC3 \\
 &+ W_{UA2} \times UA2 + W_{UA3} \times UA3 + W_{PD2} \times PD2 \\
 &+ W_{PD3} \times PD3 + W_{AD2} \times AD2 + W_{AD3} \times AD3
 \end{aligned}$$

where the variables above are defined below in Table 5 and Table 6:

Table 5 EQ-5D Variable Definitions

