Condition	Condition Code (Possible Values: 0 and 1)	Weight Name
Full health (11111)		W_FH
At least one 2 or 3 (N2)	N2	W_N2
At least one 3 (N3)	N3	W_N3
Mobility = 2	MO2	W_MO2
Mobility = 3	MO3	W_MO3
Self Care = 2	SC2	W_SC2
Self Care = 3	SC3	W_SC3
Usual Activities = 2	UA2	W_UA2

Condition	Condition Code (Possible Values: 0 and 1)	Weight Name
Usual Activities = 3	UA3	W_UA3
Pain/Discomfort = 2	PD2	W_PD2
Pain/Discomfort = 3	PD3	W_PD3
Anxiety/Depression = 2	AD2	W_AD2
Anxiety/Depression = 3	AD3	W_AD3

Table 6 EQ-5D VAS Value Sets (Excluding Germany)

Weight Name	Belgium	Denmark	Europe	Finland	New Zealand	Slovenia	Spain	UK
W_FH	1	1	1	1	1	1	1	1
W_N2	-0.152	-0.225	-0.1279	-0.158	-0.2041	-0.128	-0.1502	-0.155
W_N3	-0.256	0	-0.2288	0	-0.2165	0	-0.2119	-0.215
W_MO2	-0.074	-0.126	-0.0659	-0.058	-0.0753	-0.206	-0.0897	-0.071
W_MO3	-0.148	-0.252	-0.1829	-0.230	-0.1506	-0.412	-0.1794	-0.182
W_SC2	-0.083	-0.112	-0.1173	-0.098	-0.0714	-0.093	-0.1012	-0.093
W_SC3	-0.166	-0.224	-0.1559	-0.143	-0.1428	-0.186	-0.2024	-0.145
W_UA2	-0.031	-0.064	-0.0264	-0.047	-0.0136	-0.054	-0.0551	-0.031
W_UA3	-0.062	-0.128	-0.0860	-0.131	-0.0272	-0.108	-0.1102	-0.081
W_PD2	-0.084	-0.078	-0.0930	-0.111	-0.0798	-0.111	-0.0596	-0.084
W_PD3	-0.168	-0.156	-0.1637	-0.153	-0.1596	-0.222	-0.1192	-0.171
W_AD2	-0.103	-0.091	-0.0891	-0.160	-0.0920	-0.093	-0.0512	-0.063
W_AD3	-0.206	-0.182	-0.1290	-0.196	-0.1840	-0.186	-0.1024	-0.124

- For Germany, the utility total score using the “VAS” value set can be derived as:

Utility Total Score

$$\begin{aligned}
 &= W_{FH} \times W_{N2}^{N2} \times W_{MO2}^{MO2} \\
 &\quad \times W_{MO3}^{MO3} \times W_{SC2}^{SC2} \times W_{SC3}^{SC3} \\
 &\quad \times W_{UA2}^{UA2} \times W_{UA3}^{UA3} \\
 &\quad \times W_{PD2}^{PD2} \times W_{PD3}^{PD3} \times W_{AD2}^{AD2} \\
 &\quad \times W_{AD3}^{AD3}
 \end{aligned}$$

where the variables above are defined in Table 5 and Table 7:

Table 7 EQ-5D Vas Values for Germany

Weight Name	Germany
W_FH	1
W_N2	0.9256
W_MO2	0.9447
W_MO3	0.3927
W_SC2	0.808
W_SC3	0.4702
W_UA2	0.8803
W_UA3	0.5538
W_PD2	0.9745
W_PD3	0.4671
W_AD2	0.8174
W_AD3	0.4682

- For all countries excluding the US, the utility total score using “TTO” value sets can be derived as:

Utility Total Score

$$\begin{aligned}
 &= W_{FH} + W_{N2} \times N2 + W_{N3} \times N3 + W_{MO2} \times MO2 \\
 &+ W_{MO3} \times MO3 + W_{SC2} \times SC2 + W_{SC3} \times SC3 \\
 &+ W_{UA2} \times UA2 + W_{UA3} \times UA3 + W_{PD2} \times PD2 \\

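### SAP 7.2.4 describes a five-level EQ-5D but scores it with three-level weights, while the protocol specifies three levels; the version administered must be settled before scoring

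*SAP*

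**What the plan says.** SAP 7.2.4 opens with a five-level instrument. For each of five dimensions, "respondents select which statement best describes their health on that day from a possible 5 options of increasing levels of severity". The options are labelled from no problems to extreme problems and scored 1 to 5. The five scores are joined into a five-digit state, "allowing for a total of 3125 health states".

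The same section then derives the utility total score. Table 5 defines one indicator per dimension for level 2 and one for level 3; the last entry is "Anxiety/Depression = 3". It adds N2, which applies when any dimension is at 2 or 3, and N3, which applies when any dimension is at 3. Tables 6 to 10 give the weights. No dimension has a weight for level 4 or 5, and no mapping from five levels to three is given. On the choice of value set, "the base case will be the United Kingdom valuation set", with other country sets applied as available; scores are derived from both VAS and TTO sets.

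Protocol 10.5.1 describes the dimensions as "mobility, self-care, usual activities, pain/discomfort, and anxiety/depression each with 3 levels". The protocol's Summary of Changes (section 25) shows that this wording is deliberate: "Description of EQ-5D questionnaire amended to reflect 3 levels for each of the 5 measured dimensions", with the stated purpose of correcting an error. SAP section 13 cites that same amended protocol. SAP 5.8, which lists departures from the protocol's planned analysis, does not mention the EQ-5D.

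**The concern.** The item coding and the scoring rule within one SAP section belong to questionnaires with different numbers of levels. This is not a single mistyped digit, because the number of options, the five severity labels and the state count all agree on five levels.

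A programmer who follows the section literally would pass codes 1 to 5 into formulas that recognise only 2 and 3. Codes 4 and 5 would fall through without an error message and, in most of the value sets, cost nothing.

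The utility is tested for change from baseline within and between arms by the method of SAP 7.2.1. That method selects changes larger than half the baseline standard deviation. A score that rises as health worsens would therefore distort the change scores, the selection threshold and the set of subjects who enter the tests.

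**Working it through.** **Inputs.** Levels and state count: SAP 7.2.4 (five; 3125) and Protocol 10.5.1 (three). Indicators: SAP Table 5. UK TTO weights, SAP Table 8: N2 -0.081, N3 -0.269; level 2: mobility -0.069, self-care -0.104, usual activities -0.036, pain -0.123, anxiety -0.071; level 3: -0.314, -0.214, -0.094, -0.386, -0.236 in the same order. US extra terms: SAP Table 9.

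**State counts.** States = levels^dimensions.
- Five levels: 5^5 = 3125, which reproduces the SAP figure.
- Three levels: 3^5 = 243.
- Five-level states containing at least one 4 or 5: 3125 - 243 = 2882.
- Impaired states made only of levels 1, 4 and 5: 3^5 - 1 = 242.

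**Literal scoring, UK TTO.** Utility = 1 + N2 term + N3 term + dimension terms.

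| State | Calculation | Utility |
|---|---|---|
| 11111 | no term | 1.000 |
| 22222 | 1 - 0.081 - 0.069 - 0.104 - 0.036 - 0.123 - 0.071 | 0.516 |
| 33333 | 1 - 0.081 - 0.269 - 0.314 - 0.214 - 0.094 - 0.386 - 0.236 | -0.594 |
| 44444, 55555 | no term | 1.000 |
| 11121 | 1 - 0.081 - 0.123 | 0.796 |
| 11131 | 1 - 0.081 - 0.269 - 0.386 | 0.264 |
| 11141, 11151 | no term | 1.000 |
| 21151 | 1 - 0.081 - 0.069 | 0.850 |

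The utility falls from level 1 to level 3 and then returns to 1.000 at levels 4 and 5. All 242 impaired states made only of 1, 4 and 5 score exactly 1.000. The other 2882 - 242 = 2640 states with a 4 or 5 also contain a 2 or 3, and lose only the decrements for those levels, as 21151 shows.

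**Other value sets.**
- UK VAS (Table 6): 33333 = 1 - 0.155 - 0.215 - 0.182 - 0.145 - 0.081 - 0.171 - 0.124 = -0.073; 55555 = 1.000.
- German VAS (Table 7, multiplicative): 33333 = 0.9256 × 0.3927 × 0.4702 × 0.5538 × 0.4671 × 0.4682 = 0.0207; 55555 = 1.000.
- US TTO (Tables 9 and 10): D1 counts movements away from full health beyond the first, at +0.140 each. If it counts any dimension above level 1, 55555 has D1 = 4 and scores 1 + 4 × 0.140 = 1.56, above full health. If it counts only levels 2 and 3, 55555 scores 1.00.

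**If the data are three-level.** Only codes 1 to 3 occur, all 243 states are covered, and the worst state 33333 scores -0.594 under UK TTO. The scoring rule then works as intended.

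**The case against.** The strongest reply is that nothing shows the diary ever delivered a code of 4 or 5. The protocol says three levels and was amended expressly to say so. Every value set in the SAP is built for three levels. The silence of SAP 5.8 is what one would expect if the three-level form was kept. On that reading one descriptive paragraph is wrong and no score changes. This stands as far as it goes: it makes the three-level branch the more likely one. It does not settle the matter, because the diary specification is not in the documents, and it does not make the section correct.

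Four stronger readings are tempting and are not supported.
- A reader might infer that the trial's EQ-5D utilities are wrong. That follows only if five-level responses were collected.
- A reader might take 2882 as the number of mis-scored states. It counts states containing a 4 or 5. On a five-level reading, level 3 (moderate) would also receive the weight of the worst level of a three-level scale, so states without a 4 or 5 could be mis-scored too. Counts of states say nothing about how often subjects report them. Newly recruited subjects need a Karnofsky score of at least 60 (Protocol 9.1.2), so 44444 and 55555 illustrate the formula rather than expected data.
- A reader might say that levels 4 and 5 trigger no term in any formula. The US D1 term may be triggered.
- A reader might treat the utility as a firmly secondary endpoint. SAP 7.2.4 calls it both secondary and exploratory, and the EQ-5D appears under the secondary objectives, but the outcome-measure lists (Protocol 8.4.3, SAP 3.1.3) place it under exploratory only.

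**Conclusion.** The inconsistency is certain: within SAP 7.2.4, and between that section and Protocol 10.5.1. It is an error as written rather than a missing detail, because the coding and scoring rules taken together give a non-monotone utility.

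Its effect depends on the form administered. With five-level data scored literally, a subject going from moderate to extreme pain alone would move from 0.264 to 1.000 under UK TTO, an apparent gain of 0.736 for a deterioration. With three-level data the effect on the results is nil, and the error is confined to the item coding and the state count. The documents lean towards the second case but do not establish it.

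The outcome at stake is the EQ-5D utility. The primary endpoint is unaffected, and so is the separately reported EQ visual analogue score. The point should be corrected, but it does not threaten the trial's main conclusion.

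**What to change.** Align SAP 7.2.4 with the protocol: three levels per dimension, codes 1 to 3, 243 states. Add a programmed check that rejects any code outside 1 to 3 before scoring, so that a five-level export cannot pass silently.

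Confirm against the vendor's diary specification which form was loaded. If it was the five-level form, record that departure in SAP 5.8 and do not score with Tables 5 to 10; specify a value set or a mapping that covers all five levels.

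A minor correction can go in at the same time: Table 10 is used in the text as the US TTO set but its title says VAS, so retitle it.

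The cost is a few lines of SAP wording and one range check. A different value-set table is needed only if the five-level form was used.

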7.2.5 Physical Activity

Information on subject physical activity levels are obtained from electronic patient diaries as supplied by the third party vendor eRT.

Only days with more than 15 minutes of exercise are recorded in the subject diaries as part of the physical activity recording.

The per subject total number of physical activity days should be summarized by level of exercise (mild, moderate or strenuous) by using descriptive statistics.

The change in days of physical activity participation from baseline to completion between the two treatment arms will be assessed by descriptive statistics (point estimates and their 95% CIs) only.

7.2.6 Weigh-adjusted Consumption of BAX 855

Derivations and definitions for weigh-adjusted consumption of BAX 855 is discussed in Section 6.5: Extent of Exposure.

The weight-adjusted consumption fo BAX 855 will be summarized in a table, using descriptive statistics only.

7.2.7 Health Resource Use

The following information is obtained from the subject diaries as provided by the third party vendor eRT.

- Health resource events and usage.

The following derivations will be made based of the subject diary reported results:

- Number of days in hospital should be calculated for a subject by summing all of the individual durations (days), a subject was hospitalized.
- Number of days unable to go to school or work should be calculated by summing the number of days as indicated in the subject diaries.

- Number of days unable to carry out all usual activities should be calculated by summing the number of days as indicated in the subject diaries.

Within treatment arm change and between treatment arm change in Health resource usage between baseline and completion will be tested for any statistical significant differences in a similar manner as described in Section 7.2.1: Haemophilia Joint Health Score (HJHS) Questionnaire.

7.2.8 Surgery

Subject listings will be presented for the following surgery related items using the SGAS:

- Surgical report.
- Preoperative FVIII substitution plan (including modifications).
- Estimated and observed blood loss (including drain removal blood loss).
- Hemostatic efficacy assessments.
- Drain removal.
- Postoperative prophylaxis.
- Transfusion Requirements.

Summary tables containing descriptive statistics will be presented for surgery related blood loss and transfusion requirements using the SAS by age group.

The following information items are obtained from the eCRF:

- Surgical report information (Surgical Report eCRF panel).
- Preoperative FVIII substitution information (Preoperative FVIII Substitution Plan and Modifications of Preoperative FVIII Substitution Plan eCRF panels).
- Surgery related blood loss (Estimated Blood Loss, Surgical Report and Post-Operative 24 Hours/Drain removal Blood loss eCRF panels).
- Postoperative prophylaxis (Postoperative Prophylaxis eCRF panel).
- Transfusion requirements (Transfusion Requirements eCRF panel).

